### 4.3 Sample Size Calculations and Power Considerations

Assumptions used for sample size calculation were estimated from Phase 2 Dose Escalation Study 171-7151-201 (6).

Sample size calculations were performed on the basis of the formulas for testing superiority in term of means difference and odds ratio of Wang and Chow (7, 8).

All the hypothesis tests for the primary endpoints have to be performed at the same significance level  $\alpha=0.05$  two-sided and the failure to reject a null hypothesis will imply the failure of rejecting of all the subsequent null hypotheses.

In order to keep the overall Type II error  $\beta=0.1$  for the whole study, the sample sizes for the three hypothesis tests on the primary endpoints were calculated considering an individual Type II error  $\beta=0.033$  (3).

The hypothesis tests for the secondary endpoint will be performed at the same significance level  $\alpha=0.05$  two-sided of the primary endpoints if and only if all the null hypotheses on the primary endpoints are rejected and the failure to reject a null hypothesis will imply the failure of rejecting of all the subsequent null hypotheses. The sample sizes for the four hypothesis tests on the secondary endpoints were calculated considering an individual Type II error  $\beta=0.1$ .

Based on the previous assumptions, at least 350 subjects in each treatment group (CB-03-01 1% BID and vehicle BID) were included into each Phase 3 study to provide sufficient power (90%) with the chosen primary endpoints as this approach would:

- allow a reasonable allowance for non-completers and to provide a more meaningful number of subjects exposed to CB-03-01 cream in the safety population of the program and
- be adequate for investigating with a sufficient power the secondary endpoint.

Details of the calculations are reported in the following sections.

**4.3.1 Proportion of subjects in each treatment group with at least a two-point reduction in IGA compared to Baseline AND an IGA score of 0 (clear) or 1 (almost clear) at Week 12**

$$N_{\text{TEST}} = N_{\text{VEHICLE}} = \frac{(z_{\alpha/2} + z_{\beta})^2}{(\log(\text{OR}_{2p(0,1)}))^2} \left( \frac{1}{\pi_{2p(0,1),\text{TEST}}(1 - \pi_{2p(0,1),\text{TEST}})} + \frac{1}{\pi_{2p(0,1),\text{VEHICLE}}(1 - \pi_{2p(0,1),\text{VEHICLE}})} \right)$$

A post-hoc analysis of the data collected in the Phase 2 Dose Escalation Study 171-7151-201 (6) performed only for the subjects with 30-75 inflammatory lesions and 30-100 non-inflammatory lesions at baseline provided the following results for the proportion of success and the related sample size estimation.

	TEST	VEHICLE
Success	3 (12.50%)	0 (0.00%)
Failure	21 (87.50%)	22 (100.00%)

Since the number of success is zero for VEHICLE, a continuity correction (Haldane correction) was applied to each cell in the previous table in order to calculate the odds ratio:

	TEST	VEHICLE
Success	3.5 (14.00%)	0.5 (2.17%)
Failure	21.5 (86.00%)	22.5 (97.83%)

$$\text{OR}_{2p(0,1),TV} = \frac{\pi_{2p(0,1),\text{TEST}}(1 - \pi_{2p(0,1),\text{VEHICLE}})}{\pi_{2p(0,1),\text{VEHICLE}}(1 - \pi_{2p(0,1),\text{TEST}})} = 7.3256$$

$$\alpha = 0.05 \text{ two - sided}, \beta = 0.033 \Rightarrow N_{\text{TEST}} = N_{\text{VEHICLE}} = 202$$

**202 subjects per group** should be enrolled in order to have 202 subjects per group included into the ITT Set.

**4.3.2 Absolute change from baseline in NILC in each treatment group at Week 12**

$$N_{\text{TEST}} = N_{\text{VEHICLE}} = \frac{2\sigma^2(z_{\alpha/2} + z_{\beta})^2}{(\mu_{\text{NILC,TEST}} - \mu_{\text{NILC,VEHICLE}})^2}$$

A post-hoc analysis of the data collected in the Phase 2 Dose Escalation Study 171-7151-201 (6) performed only for the subjects with 30-75 inflammatory lesions and 30-100 non-inflammatory lesions at baseline provided the following results for the least square means (i.e. the means obtained after having controlled for the fixed effects and the covariate of the ANCOVA) of the absolute change from baseline in non-inflammatory lesions count and for the related sample size estimation.

	Number of subjects	Least Square Mean
TEST	24	-22.398746
VEHICLE	22	-0.924803

Considering a mean absolute change from baseline in non-inflammatory lesions count of **-22** for TEST treatment group and **-1** for VEHICLE treatment group and a common standard deviation of **17**, we obtain the following estimate of the sample size.

$$\alpha = 0.05 \text{ two - sided}, \beta = 0.033, \mu_{\text{ILC,TEST}} = -22, \mu_{\text{ILC,VEHICLE}} = -1, \sigma = 17$$

$$N_{\text{TEST}} = N_{\text{VEHICLE}} = 19$$

**19 subjects per group** should be enrolled in order to have 19 subjects per group included into the ITT Set.

#### 4.3.3 Absolute change from Baseline in ILC in each treatment group at Week 12

$$N_{\text{TEST}} = N_{\text{VEHICLE}} = \frac{2\sigma^2(z_{\alpha/2} + z_{\beta})^2}{(\mu_{\text{ILC,TEST}} - \mu_{\text{ILC,VEHICLE}})^2}$$

A post-hoc analysis of the data collected in the Phase 2 Dose Escalation Study 171-7151-201 (6) performed only for the subjects with 30-75 inflammatory lesions and 30-100 non-inflammatory lesions at baseline provided the following results for the least square means (i.e. the means obtained after having controlled for the fixed effects and the covariate of the ANCOVA) of the absolute change from baseline in inflammatory lesions count and for the related sample size estimation.

	Number of subjects	Least Square Mean
TEST	24	-14.473098
VEHICLE	22	-10.621723

Considering a mean absolute change from baseline in inflammatory lesions count of **-15** for TEST treatment group and **-10** for VEHICLE treatment group and a common standard deviation of **17**, we obtain the following estimate of the sample size.

$$\alpha = 0.05 \text{ two - sided}, \beta = 0.033, \mu_{\text{ILC,TEST}} = -15, \mu_{\text{ILC,VEHICLE}} = -10, \sigma = 17$$

$$N_{\text{TEST}} = N_{\text{VEHICLE}} = 334$$

**334 subjects per group** should be enrolled in order to have 334 subjects per group included into the ITT Set.

#### 4.3.4 Absolute change from Baseline in TLC at Week 12

$$N_{\text{TEST}} = N_{\text{VEHICLE}} = \frac{2\sigma^2(z_{\alpha/2} + z_{\beta})^2}{(\mu_{\text{TLC,TEST}} - \mu_{\text{TLC,VEHICLE}})^2}$$

A post-hoc analysis of the data collected in the Phase 2 Dose Escalation Study 171-7151-201 (6) performed only for the subjects with 30-75 inflammatory lesions and 30-100 non-inflammatory lesions at baseline provided the following results for the least square means (i.e. the means obtained after having controlled for the fixed effects and the covariate of the ANCOVA) of the absolute change from baseline in total lesions count and for the related sample size estimation.

	Number of subjects	Least Square Mean
TEST	24	-35.7127562
VEHICLE	22	-13.0667959

Considering a mean absolute change from baseline in total lesions count of **-35** for TEST treatment group and **-13** for VEHICLE treatment group and a common standard deviation of **17**, we obtain the following estimate of the sample size.

$$\alpha = 0.05 \text{ two - sided}, \beta = 0.1, \mu_{\text{TLC,TEST}} = -35, \mu_{\text{TLC,VEHICLE}} = -13, \sigma = 17$$

$$N_{\text{TEST}} = N_{\text{VEHICLE}} = 13$$

**13 subjects per group** should be enrolled in order to have 13 subjects per group included into the ITT Set.

#### 4.3.5 Percent change from Baseline in TLC at Week 12

$$N_{\text{TEST}} = N_{\text{VEHICLE}} = \frac{2\sigma^2(z_{\alpha/2} + z_{\beta})^2}{(P_{\text{TLC,TEST}} - P_{\text{TLC,VEHICLE}})^2}$$

A post-hoc analysis of the data collected in the Phase 2 Dose Escalation Study 171-7151-201 (6) performed only for the subjects with 30-75 inflammatory lesions and 30-100 non-inflammatory lesions at baseline provided the following results for the least square means (i.e. the means obtained after having controlled for the fixed effects and the covariate of the ANCOVA) of the percent change from baseline in total lesions count and for the related sample size estimation.

	Number of subjects	Least Square Mean
TEST	24	-35.455503
VEHICLE	22	-14.144333

Considering a mean percent change from baseline in total lesions count of **-35** for TEST treatment group and **-14** for VEHICLE treatment group and a common standard deviation of **40**, we obtain the following estimate of the sample size.

$$\alpha = 0.05 \text{ two - sided}, \beta = 0.1, \mu_{\text{TLC,TEST}} = -35, \mu_{\text{TLC,VEHICLE}} = -14, \sigma = 40$$

$$N_{\text{TEST}} = N_{\text{VEHICLE}} = 77$$

**77 subjects per group** should be enrolled in order to have 77 subjects per group included into the ITT Set.

#### 4.3.6 Percent change from Baseline in NILC at Week 12

$$N_{\text{TEST}} = N_{\text{VEHICLE}} = \frac{2\sigma^2(z_{\alpha/2} + z_{\beta})^2}{(P_{\text{NILC,TEST}} - P_{\text{NILC,VEHICLE}})^2}$$

A post-hoc analysis of the data collected in the Phase 2 Dose Escalation Study 171-7151-201 (6) performed only for the subjects with 30-75 inflammatory lesions and 30-100 non-inflammatory lesions at baseline provided the following results for the least square means (i.e. the means obtained after having controlled for the fixed effects and the covariate of the ANCOVA) of the percent change from baseline in non-inflammatory lesions count and for the related sample size estimation.

	Number of subjects	Least Square Mean
TEST	24	-33.718297
VEHICLE	22	-5.133111

Considering a mean percent change from baseline in non-inflammatory lesions count of **-33** for TEST treatment group and **-5** for VEHICLE treatment group and a common standard deviation of **40**, we obtain the following estimate of the sample size.

$$\alpha = 0.05 \text{ two - sided}, \beta = 0.1, \mu_{\text{TLC,TEST}} = -33, \mu_{\text{TLC,VEHICLE}} = -5, \sigma = 40$$

$$N_{\text{TEST}} = N_{\text{VEHICLE}} = 43$$

**43 subjects per group** should be enrolled in order to have 43 subjects per group included into the ITT Set.

#### 4.3.7 Percent change from Baseline in ILC at Week 12

$$N_{\text{TEST}} = N_{\text{VEHICLE}} = \frac{2\sigma^2(z_{\alpha/2} + z_{\beta})^2}{(P_{\text{ILC,TEST}} - P_{\text{ILC,VEHICLE}})^2}$$

A post-hoc analysis of the data collected in the Phase 2 Dose Escalation Study 171-7151-201 (6) performed only for the subjects with 30-75 inflammatory lesions and 30-100 inflammatory lesions at baseline provided the following results for the least square means (i.e. the means obtained after having controlled for the fixed effects and the covariate of the ANCOVA) of

the percent change from baseline in inflammatory lesions count and for the related sample size estimation.

	Number of subjects	Least Square Mean
TEST	24	-37.657976
VEHICLE	22	-23.450604

Considering a mean percent change from baseline in inflammatory lesions count of **-37** for TEST treatment group and **-23** for VEHICLE treatment group and a common standard deviation of **40**, we obtain the following estimate of the sample size.

$$\alpha = 0.05 \text{ two - sided}, \beta = 0.1, \mu_{\text{TLC,TEST}} = -37, \mu_{\text{TLC,VEHICLE}} = -23, \sigma = 40$$

$$N_{\text{TEST}} = N_{\text{VEHICLE}} = 172$$

**172 subjects per group** should be enrolled in order to have 172 subjects per group included into the ITT Set.

## 5. BLINDING/UNBLINDING AND BLIND REVIEW

Blinding is important for the integrity of this clinical drug trial. However, the blind may be broken in the event of a medical emergency in a subject, in which knowledge of the test article identity is critical to the subject's management. Before breaking the blind for a subject, the investigator should determine that the information is necessary (i.e., that it alters the subject's immediate management). In many cases, particularly when the emergency is clearly not test article related, the problem may be effectively managed by assuming that the subject is receiving active product without the need for unblinding. The need to break the blind had first to be discussed with the responsible Medical Monitor and the best method to do this was determined.

Data collected during the study will be revised in blind, the assignment of subjects to the analysis sets (ITT, PP and Safety) and the definition of the analysis centers (see section 6.5) will be performed before the database lock during the blind review meeting/conference.

The review team will be composed only of people not directly involved in the clinical phase of the trial in order to safeguard their blindness to the administered treatments.

## 6. STATISTICAL METHODS

All statistical analysis will be performed using SAS for Windows Version 9.3 (TS1M1) (9) (or higher).

The data documented in this trial and the parameters measured will be summarised using classic descriptive statistics: mean, standard deviation, percent coefficient of variation (CV%), minimum, median and maximum values for quantitative variables. Frequency counts and percentage of subjects within each category are provided for categorical data. Summaries will be provided for each treatment group. Data not available will be managed according to the procedure described in the paragraph 6.4.

### 6.1 Tables, Listings and Figures layout

Tables and Listings will be provided according to the following settings:

- Background: White
- Foreground: Black
- Font face: Times
- Font style: Roman
- Font size: 10 pt
- Font weight: Medium (data, footers and notes), Bold (titles and headers)
- Font width: Normal
- Layout: Landscape
- Top Margin: 0.8 cm
- Bottom Margin: 0.8 cm
- Left Margin: 0.8 cm
- Right Margin: 0.8 cm
- Test label: CB-03-01
- Placebo label: Vehicle
- Date format: ddMMMyyyy

- Means, standard deviations, percent coefficient of variations, medians, lower confidence limits and upper confidence limits will be rounded to one digit more than the original data
- Minima and maxima will keep the same number of decimal digits as the source values
- p-values will be rounded to the fourth decimal digit and will be flagged by an asterisk (\*) in case of statistical significance (i.e. p-value < 0.05 or, in case of center by treatment interaction, p-value < 0.10). p-values lower than 0.0001 will be reported as “<.0001 \*”.

The data and results of CB-03-01 will be presented before the data and results of Vehicle in all listings and tables.

## 6.2 Analysis sets

The following analysis sets will be defined:

1. Intent-to-Treat Set (ITT): all randomised subjects. This analysis set will be used for primary analyses and sensitivity analyses.
2. Per Protocol Set (PP): all randomised subjects who will fulfil the study protocol requirements in terms of investigational medicinal product intake and collection of primary efficacy data, will not have any inclusion/exclusion criteria violation and with no major deviations that may affect study results. This analysis set will be used for sensitivity analyses.
3. Safety Set: all subjects who will receive at least one dose of the test article. This analysis set will be used for safety analyses.

### 6.2.1 Exclusion from the Per Protocol Set

Reasons for the exclusion from the Per Protocol Set include the following:

1. lack of compliance to the test article (subjects with an overall compliance not evaluable due to missing data or less than 80% as defined in paragraph 6.3);
2. exposure to an test article different from the one assigned to the subject;
3. lack of the primary variables assessments at Baseline or at Week 12;
4. failure to satisfy any inclusion/exclusion criteria (eligibility violations);
5. intake of prohibited medications.

The precise reasons for excluding subjects from the per protocol set will be fully defined and documented in the blind review meeting/conference report before breaking the blind.

### 6.3 Evaluation of Treatment Compliance

Compliance to the test article will be evaluated at each visit and overall according to the following formula:

$$\text{Compliance} = 100 \times \frac{\text{Number of actual applications}}{\text{Number of scheduled applications}}$$

Non-compliance will be defined as a compliance value less than 80% and subjects with an overall compliance not evaluable due to missing data or less than 80% will be excluded from the Per Protocol Set (see paragraph 6.2.1).

### 6.4 Handling of missing data

#### 6.4.1 Methods for replacing missing data

1. Multiple imputation (MI) under missing at random (MAR) assumption: multiple imputation is a general approach to the problem of missing data that aims to allow for the uncertainty about the missing data by creating several different plausible imputed data sets and appropriately combining results obtained from each of them. Missing at random (MAR) approach assumes that any systematic difference between the missing values and the observed values can be explained by differences in observed data. The use of multiple imputation under MAR assumption provides unbiased estimations of the parameters and allows to evaluate the uncertainty of parameters' estimation due to the presence of missing data.

A Markov Chain Monte Carlo (MCMC) method that assumes multivariate normality will be used to impute all the missing values. In order to prevent a power falloff due to choosing a number of imputations too small, 10 imputations will be performed (10).

The multiple imputation procedure will be implemented by using the MI procedure of the SAS system with the following options:

- NIMPUTE=10
- SEED=1
- ROUND=0
- MINMAXITER=10000000

and the following MCMC statement:

- MCMC IMPUTE=FULL CHAIN=SINGLE INITIAL=EM (BOOTSTRAP=0.9 CONVERGE=1E-6 ITPRINT MAXITER=1000)

A unique imputation process will be performed without taking into account the treatment arm.

The imputed data sets will be then analysed with the MIANALYZE procedure of the SAS system with the following options:

- ALPHA=0.05
- EDF=number of subjects of the ITT set - number of estimated parameters (including intercept)]

Type-III analyses obtained from multiple imputations will be combined according to the method proposed by Binhuan Wang and Yixin Fang (11).

2. Missing as Worst Value (MWV): for each subject, missing values of a variable will be replaced with the worst value (failure in case of dichotomous variables or the higher value collected in the study for lesions counting) of that variable regardless of the treatment arm.
3. Worst Case (WC): for each subject, missing values of a variable will be replaced with the worst value (failure in case of dichotomous variables or the higher value collected in the study for lesions counting) of that variable if the subject is assigned to the CB-03-01 arm and with the best value of that variable (success in case of dichotomous variables or the lower value collected in the study for lesions counting) if the subject is assigned to the Vehicle arm.
4. Last Observation Carried Forward (LOCF): for each subject, missing values of a variable are replaced by the last observed value of that variable.
5. Baseline Observation Carried Forward (BOCF): for each subject, missing values of a variable are replaced by the baseline observed value of that variable.

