#### **6.4.2 Replacement rules for each analysis set**

1. Intent-to-Treat Set (ITT): all missing values of the primary endpoints will be replaced according to the MI under MAR assumption method for the primary analysis and according to the MWV, WC, LOCF and BOCF methods in order to perform four distinct sensitivity analyses. Missing values of the secondary endpoints will be replaced according to the MI under MAR assumption method.
2. Per Protocol Set (PP): no replacement of missing data is required for the primary and secondary endpoints.
3. Safety Set: no replacement of missing data is required for the safety endpoints.

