#### **6.7.1 Primary efficacy analysis**

##### **6.7.1.1 Proportion of subjects in each treatment group with at least a two-point reduction in IGA compared to Baseline AND an IGA score of 0 (clear) or 1 (almost clear) at Week 12 - ITT**

A logistic regression model with treatment and analysis center as fixed effects will be used to compare the proportion of subjects in each treatment group with at least a two-point reduction in IGA AND an IGA score of 0 (clear) or 1 (almost clear) at Week 12 ( $\pi_{2p(0,1)}$ ). Subjects will be analysed according to the treatment they were assigned to (ITT) and missing data will be replaced using a multiple imputation (MI) under missing at random (MAR) assumption.

The adjusted odds ratio of the comparison of  $\pi_{2p(0,1)}$  between CB-03-01 and Vehicle and its 95% confidence interval will be derived from the regression model (Table 14.2.2.1).

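### The primary multiple imputation leaves out treatment arm, so any Week 12 effect not visible in a subject's observed data is imputed as zero, and the method is not unbiased as the SAP states

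*SAP*

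**What the plan says.** SAP 6.4.1, item 1, describes multiple imputation under MAR and says of it: "The use of multiple imputation under MAR assumption provides unbiased estimations of the parameters". It then specifies a multivariate-normal MCMC method with 10 imputations and adds: "A unique imputation process will be performed without taking into account the treatment arm". It does not list the visits or variables in the imputation model, or say whether the IGA score or the success status is imputed.

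SAP 6.4.2 makes this the main method: "all missing values of the primary endpoints will be replaced according to the MI under MAR assumption method for the primary analysis". The secondary endpoints use it too, and the percent changes are calculated from the imputed counts (SAP 6.7.2.2 to 6.7.2.4).

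All the efficacy models contain treatment. For P1: "A logistic regression model with treatment and analysis center as fixed effects will be used". P2, P3 and S1 to S4 use ANCOVA with treatment, analysis center and the baseline count (SAP 6.7.1.2 to 6.7.2.4).

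The planned sensitivity analyses are per-protocol, missing as worst value (MWV), worst case (WC), LOCF and BOCF (SAP 6.7.3). None repeats the multiple imputation with arm included. Protocol 17.3.1.3 calls for multiple imputation under MAR and does not mention leaving arm out.

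**The concern.** The imputation model omits the variable whose effect the analysis estimates. Take two subjects with the same baseline and interim values, one on active and one on vehicle, both without Week 12 data. Their imputed values come from the same distribution. Whatever the treatment does by Week 12 beyond what their earlier data show is set to zero. This happens even when data are missing completely at random, so the cause is the imputation model and not a failure of MAR. MAR as the SAP defines it conditions on observed data, and arm is observed for every randomized subject.

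At stake are the reported effect sizes for P1 to P3, which carry over to S1 to S4, and some power on P3. P3 set the sample size, and it must be rejected before any secondary endpoint is tested (SAP 4.2).

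**Working it through.** **Inputs from the documents.** P1: 14.00% against 2.17%, odds ratio 7.3256. P2: -22 against -1, SD 17. P3: -15 against -10, SD 17. Alpha is 0.05 two-sided, beta 0.033 per primary test, allocation 1:1, at least 350 per arm (SAP 4.3). Protocol 17.2 prints -14 and -11 for P3. Only -15 and -10 (Protocol synopsis, SAP 4.3.3) reproduce the stated sample size, so those are used.

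**The plan's own figures.** (z_0.025 + z_0.033)² = (1.960 + 1.838)² = 14.43.
- P3: 2 × 17² × 14.43 / 5² = 333.6, so 334. Matches.
- P2: 2 × 17² × 14.43 / 21² = 18.9, so 19. Matches.
- P1: 14.43 / (ln 7.3256)² × (1/(0.14 × 0.86) + 1/(0.0217 × 0.9783)) = 201.3, so 202. Matches.

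**Assumptions.** The documents give no missing rate; 5, 10 and 20% are assumed. Visit correlations, the time course of the effect and the timing of dropout are also assumed.

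**Upper bound: no post-baseline data used.** Let m_T and m_V be the missing fractions on active and vehicle, and w the active share of observed subjects. The pooled imputation gives

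difference = δ × [1 - m_T(1 - w) - m_V·w],

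which is δ(1 - m) when missingness is equal. For P3 at m = 0.10, missing subjects in both arms are imputed around -12.5. Active becomes 0.9 × (-15) + 0.1 × (-12.5) = -14.75 and vehicle becomes 0.9 × (-10) + 0.1 × (-12.5) = -10.25, a difference of 4.50.

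For P1 the pooled proportion is (14.00 + 2.17)/2 = 8.09%. At m = 0.10, active is 0.9 × 14.00 + 0.1 × 8.09 = 13.41% and vehicle is 0.9 × 2.17 + 0.1 × 8.09 = 2.77%, giving an odds ratio of 5.45. This mixes proportions in closed form; it is not the SAP's normal model.

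**Weeks 4 and 8 used.** This was simulated for monotone dropout with an effect that grows over the visits. Point estimates come from large samples (at least 400,000 per arm). P3 power comes from 350 per arm, 10 imputations, Rubin's rules and 1,500 replicates.

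| Quantity | 5% missing | 10% | 20% |
|---|---|---|---|
| P3 (true 5), no history, arm-blind | 4.75 | 4.50 | 4.00 |
| P3, Weeks 4/8 used, arm-blind | 4.7-4.8 | 4.6 | 4.2 |
| P2 (true 21), no history, arm-blind | 19.95 | 18.9 | 16.8 |
| P2, Weeks 4/8 used, arm-blind | 20.2 | 19.3 | 17.7 |
| P1 OR (true 7.33), no history, arm-blind | 6.27 | 5.45 | 4.23 |
| P1 OR, Weeks 4/8 used, arm-blind | 6.5-6.7 | 5.7-5.9 | 4.7-4.9 |
| P3 power, Weeks 4/8 used, arm-blind | 96.2% | 93.7% | 87.1% |
| P3 power, Weeks 4/8 used, with arm | 96.9% | 95.2% | 93.2% |
| Rejection with no effect at any visit, arm-blind | 3.7% | 3.1% | 1.9% |
| Rejection with no effect at any visit, with arm | 4.8% | 5.2% | 4.9% |

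Monte Carlo 95% error on a single power figure is about 1 point near 96% and 1.7 points near 87%. With arm included, P3 stays at about 5.0 and P2 at about 21.0.

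**Standard errors.** At 20% missing, the arm-blind Rubin SE for P3 is 1.41, while that estimator's actual sampling SD is 1.18. The test is therefore conservative as well as shrunk. With arm the two agree (1.43 and 1.41).

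**Do the planned sensitivity analyses reveal it?** BOCF and MWV treat missing subjects alike in both arms, so in expectation they also give 5(1 - m). LOCF uses another rule: "missing values of a variable are replaced by the last observed value of that variable". In a separate simulation (366 per arm, i.e. 732/2; effects of 2, 3.5 and 5 lesions at Weeks 4, 8 and 12 assumed), LOCF matched arm-blind imputation when no post-baseline data existed (4.50 for both at 10% missing). When Weeks 4 and 8 were observed, LOCF shrank P3 by about half as much: 4.84 against 4.74 at 10%, and 4.73 against 4.51 at 20%. WC is extreme by design. Per-protocol changes the population, since it removes subjects for, among other reasons, "lack of compliance to the test article".

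**The case against.** The strongest reply is that the choice is explicit, prespecified and cautious. With no effect at any visit the test rejects less than 5% of the time, so a positive result stays credible. That stands, and it limits how serious the point is. A reader might infer a threat to a positive trial; the documents and figures do not support that.

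A reader might also infer that the bias is always toward no effect. It is not. The direction requires the Week 12 effect that remains after conditioning on history to have the same sign as the total effect. With an assumed waning effect of 10, 10 and then 5 lesions and all dropout after Week 8, arm-blind P3 was 5.24 at 10% and 5.45 at 20% missing. With a transient effect that is null at Week 12, it favoured active by 0.2 to 0.5 lesions at 5 to 20% missing, with rejection still below 5%. Nothing in the documents suggests either pattern.

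It is tempting to read the step from 334 to 350 per group as a planned missing rate of 4.6%. The SAP does not support this. It justifies 350 partly to "allow a reasonable allowance for non-completers", but also by safety exposure and power for the secondary endpoints. ITT is all randomized subjects, and SAP 4.3.3 says that 334 per group "should be enrolled in order to have 334 subjects per group included into the ITT Set", with no inflation. The missing rate is simply not stated. It may be low: early terminators are to complete the Week 12 activities (Protocol Schedule of Events footnote 1 and 13.2; SAP Study Schedule), which helps if those assessments are analysed as Week 12 values.

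The no-history rows are a bound. IGA and lesion counts are scheduled at Weeks 4 and 8, and an odds ratio of 4.23 should not be taken as the expected result. The bound cannot be excluded, because the imputation variables are not listed.

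Finally, the unbiasedness sentence can be read as a general remark about multiple imputation. It still stands as the justification for the method specified directly after it, and it is not true of that method.

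**Conclusion.** The point holds. A stated rule makes the primary estimator biased whenever part of the Week 12 effect is not visible in the imputed subjects' observed data. If that part has the same sign as the total effect, the P1 odds ratio and the differences for P2, P3 and S1 to S4 are understated. With Weeks 4 and 8 in the model, P3 is understated by about 4-6% at 5% missing (4.7-4.8 of 5) and 16% at 20% missing (4.2 of 5). The P3 power lost by leaving arm out is 0.7, 1.5 and 6.1 points at 5, 10 and 20% missing. No planned sensitivity analysis isolates the problem, and agreement with BOCF or MWV could be mistaken for robustness because they shrink the estimate too.

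The mechanism follows from the SAP text alone. The size rests on the assumed missing rates, visit correlations, effect path and dropout timing. It is small if few values are missing. It should be corrected before lock for the accuracy of the effect estimates and for P3 power, not because a false positive is more likely.

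**What to change.** By a dated SAP amendment, made before database lock by people blind to treatment, replace the arm-blind sentence in 6.4.1 with:

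> Randomized treatment arm will be included in the imputation model, together with the baseline, Week 4, Week 8 and Week 12 values of NILC and ILC, and of IGA; TLC, percent changes and IGA success will be derived from the imputed values.

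Deriving TLC matters because it is the exact sum of NILC and ILC and should not sit beside them in one normal model. SAP 6.7.2.1 and 6.7.2.4 need matching edits.

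Reword the unbiasedness sentence: under MAR given the variables in the imputation model, including arm, multiple imputation gives approximately unbiased treatment differences for the lesion counts. Make no such claim for P1. Normal imputation and rounding leave a separate bias there even with arm included: across 5 to 30% missing, the simulated odds ratio was about 6.9-7.3 if the IGA score is imputed and 5.4-7.0 if success is imputed directly.

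Keep the arm-blind run as a labelled sensitivity analysis.

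Costs:
- All 732 subjects are already enrolled (SAP 2.4) and the change is expected to move estimates away from no effect, so the blinded, dated record is essential.
- The sampling SD of the P3 estimate rises from 1.25 to 1.31 at 5% missing and from 1.18 to 1.41 at 20%.
- MAR with arm is less cautious if subjects who stop treatment lose benefit; the planned MWV, WC and BOCF analyses already address that.
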